## PROTOCOL SUMMARY

**Title:** EASSE – Eliquis Acute Stroke Safety Evaluation

The Eliquis Acute Stroke Safety Evaluation (EASSE) is an investigator initiated, prospective, open label, single arm phase IV study.

**Overall Study Aims:**

1. Demonstrate the safety of early anticoagulation with apixaban following cardioembolic stroke and TIA.
2. Document the rate of recurrent cerebrovascular ischemic events.

**Primary Outcome:** The primary endpoint is the rate of symptomatic hemorrhagic transformation (PH2) associated with clinical deterioration, defined as worsening of NIHSS score of 4 or more points within 30 days of initiating anticoagulant therapy.

**Secondary Outcome:** The major secondary endpoint is the rate of any parenchymal haemorrhage (PH1 or PH2) seen on follow-up MRI scans at  $7\pm2$  days post-enrolment. Other secondary endpoints include recurrent TIA/Ischemic Stroke within 90 days of enrolment, and systemic hemorrhagic complication rate within 90 days of enrolment

**Population:** 50 participants will be enrolled. Participants are males and females,  $\geq 18$  years of age, with TIA or ischemic stroke and a known history of or demonstrated atrial fibrillation (paroxysmal or persistent), who can be treated with apixaban following stroke.

**Phase:** IV

**Protocol Therapy:** Patients will be treated with apixaban within 14 days of symptom onset. Patients fulfilling at least two (2) of the following characteristics, will have received a reduced dose of ELIQUIS 2.5 mg twice daily: age  $\geq 80$  years, body weight  $\leq 60$  kg, or serum creatinine  $\geq 133$   $\mu\text{mol/L}$  (1.5 mg/dL). All other patients will have received 5 mg dose taken orally twice daily.

**Study Duration:** It is estimated that recruitment will take place over 2 years in the three participating centres. Enrolment is anticipated to commence by the beginning of 2017.

**Subject Participation Duration:** All patients will be assessed clinically at Day 7 and Day 90.

## 1.0 Background and Rationale

### 1.1 *Timing of Anticoagulation after Cardioembolic TIA/Stroke*

It is clearly established that patients with atrial fibrillation who have suffered a stroke/TIA are at high risk for recurrence and require long-term anticoagulation. What is unknown is the optimal timing of anticoagulation after an ischemic stroke has occurred. Following cardioembolic stroke, atrial fibrillation patients are at risk for early recurrent thrombo-embolism. Estimates of the rate of recurrent stroke in this setting vary widely. Previous studies have indicated new ischemic strokes occur at rates anywhere from 3% to 20% within two weeks of the index event. Data from the Ontario Stroke Registry demonstrated that half of the ischemic stroke cases occurred within the first 2 days after the initial event. This is the primary rationale for early anticoagulation after cardioembolic stroke. There is some evidence that early anticoagulation is associated with improved outcomes after ischemic stroke. Indeed, it has been shown that early heparin use does reduce recurrent ischemic stroke risk by 2.1%, but this is offset by a 1.7% increase in the rate of HT. Studies of low molecular weight and unfractionated heparin use in acute stroke have generally indicated these agents are associated with moderately increased risk of HT. There are currently no data indicating the frequency of HT associated with early warfarin treatment, without heparin bridging.

Based on the above evidence, current best practice guidelines recommend against urgent anticoagulation in patients with moderate to severe ischemic stroke, however, due to the elevated risk of hemorrhagic transformation (HT) immediately after stroke. A specific time point at which to begin anticoagulation is not recommended in guideline statements. This clinical equipoise has resulted in significant variation in practice patterns. Currently, most CSC physicians base the timing of anticoagulation on clinical severity and infarct size, as seen on CT scan. Most physicians will defer anticoagulation anywhere from 5 to 14 days after ischemic stroke when infarct volume is extensive. In patients with small infarct volumes, assessed with CT or MRI, however, anticoagulation is often begun within 24-72 hours of stroke onset, and in some cases immediately after clinical assessment and CT scan.

Currently, the Alliance has no data related to early use of apixaban after TIA or ischemic stroke. In ARISTOTLE, patients were not eligible for enrolment/randomization within 7 days of ischemic stroke or TIA. The contraindications section of the product monograph states apixaban should not be used in patients with 'Lesions or conditions at increased risk of clinically significant bleeding, e.g., recent cerebral infarction (ischemic or hemorrhagic)'. This is therefore an area of clinical equipoise. As with warfarin (with/without heparin bridging), stroke specialists will make individual treatment decisions, based primarily on the extent of infarction visible on CT brain scan.

Although a randomized study of delayed versus early anticoagulation with apixaban will ideally answer this question, at the moment, there is no feasibility or safety data. There is also insufficient data in the present literature to indicate what the true event rates for both symptomatic hemorrhagic transformation and recurrent cerebral ischemia are. These data can be obtained by prospectively collecting clinical and imaging data from patients who are treated, as per standard clinical practice in most Canadian stroke centres, within this 7-day period of clinical

uncertainty. The results of this registry will be used to assess the safety and feasibility of a larger randomized controlled trial of early versus delayed apixaban use after stroke/TIA.

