## 2.0 Study Objectives

### 2.1 Overall Aim and Hypothesis

The primary aim of the Eliquis Acute Stroke Safety Evaluation registry is to demonstrate the safety of early anticoagulation with apixaban following cardioembolic stroke and TIA. Safety will be established by demonstrating low rates of hemorrhage in this setting. The secondary study objective is to document the rate of recurrent cerebrovascular ischemic events. It is fully recognized that this uncontrolled registry study is not properly designed and underpowered to demonstrate a reduction in cerebrovascular ischemic events.

We hypothesize that early initiation of apixaban within the first 14 days of stroke or TIA is not associated with increased symptomatic intracranial haemorrhage.

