## 5.0 Treatment

Patients in whom apixaban is initiated within 14 days of TIA/stroke symptom onset will be included in the registry. The timing of initiation of therapy within that 14 day window will be determined by the treating physician. Patients fulfilling at least two of the following characteristics, will have received a reduced dose of ELIQUIS 2.5 mg twice daily: age  $\geq 80$  years, body weight  $\leq 60$  kg, or serum creatinine  $\geq 133$   $\mu\text{mol/L}$  (1.5 mg/dL). All other patients will have received a 5 mg dose to be taken orally twice daily.

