## 9.0 Central Imaging Adjudication and Analysis

Dicom CT and MRI data will be transferred to the Stroke Imaging Laboratory at the University of Alberta for post-processing and analysis. All image assessments will be performed using software developed specifically for CT brain image analysis (Quantomo software package, Cybertrial Inc, Calgary, AB). The extent of any objective acute and chronic ischemic changes on all CT scans will be assessed using Alberta Stroke Program Early CT Scores (ASPECTS). The extent of subacute ischemic changes will also be assessed using the day 1 MRI (Diffusion-Weighted Imaging sequences). Infarct volumes will be measured objectively using planimetric techniques. The extent of periventricular leukoarosis will also be measured using planimetric techniques and an intensity threshold algorithm included in the Quantomo software package.

[figure not shown]
All cases of hemorrhagic transformation seen on post-dabigatran treatment scans will be graded using the ECASS (European Cooperative Acute Stroke Study) hemorrhage classification scheme:

1. PH2 - parenchymal hemorrhage as a blood clot in more than 30% of the infarcted area with substantial space-occupying effect.
2. PH1 - parenchymal hemorrhage as blood clots in 30% or less of the infarcted area with some slight space-occupying effect.
3. HT2 - hemorrhagic transformation 2 - confluent petechiae within the infarcted area but no space-occupying effect.
4. HT1 - hemorrhagic transformation 1 – small petechiae along the margins of the infarct.
5. R - remote ICH, i.e. not topographically related to the infarct (most often in the contralateral hemisphere).

A symptomatic ICH (primary endpoint) will be defined as PH2, associated with an NIHSS deterioration of  $\geq 4$  points. The primary endpoint will be assessed using the day 7 MRI scan and any additional scans performed within 30 days of apixaban initiation.

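### Section 2.1 reads the safety of early anticoagulation from one uncontrolled haemorrhage rate, although physicians choose the start day largely from infarct extent and severity

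*Protocol*

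**What the plan says.** Four parts of the protocol bear on this.

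- **How the start day is chosen.** Section 1.1 says that "most CSC physicians base the timing of anticoagulation on clinical severity and infarct size, as seen on CT scan". For extensive infarcts, "Most physicians will defer anticoagulation anywhere from 5 to 14 days after ischemic stroke when infarct volume is extensive". For small infarcts, "anticoagulation is often begun within 24-72 hours of stroke onset". The same section expects this for apixaban too: "stroke specialists will make individual treatment decisions, based primarily on the extent of infarction visible on CT brain scan".
- **Who chooses it here.** Section 5.0: "The timing of initiation of therapy within that 14 day window will be determined by the treating physician". The note to 4.1 adds that the decision is independent of the registry.
- **Why the choice is related to bleeding.** Section 1.1 reports that guidelines advise against urgent anticoagulation in moderate to severe stroke "due to the elevated risk of hemorrhagic transformation (HT) immediately after stroke".
- **What is to be concluded.** The aim in 2.1 is to "demonstrate the safety of early anticoagulation with apixaban following cardioembolic stroke and TIA". Low haemorrhage rates are to establish that safety, and the hypothesis is that initiation within 14 days is not associated with more symptomatic intracranial haemorrhage. Section 2.1 concedes the uncontrolled design only for ischaemic events. Section 7.0 tests one pooled rate, with 2% as the reference.

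Section 9.0 provides for the central measurement of infarct size: "Infarct volumes will be measured objectively using planimetric techniques".

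**The concern.** The claim in 2.1 is about timing, and the hypothesis is worded as an absence of association. Both need something to compare with: other start times in like patients, or a rate without early treatment. The study has neither. In addition, the start day follows infarct extent and severity, which 1.1 links to the decision to delay and, for severity, to haemorrhagic transformation. The patients who start soonest are then likely to be those whom their physicians judged least likely to bleed.

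At stake is the use of the result. Section 1.1 says that it will inform the safety and feasibility of a larger randomised trial of early versus delayed apixaban. In such a trial the start day is assigned and no longer chosen patient by patient. A rate obtained under selected timing, but reported as the safety of early anticoagulation, could be carried into that trial as if it were the rate under assigned early start.

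**Working it through.** The protocol gives no figure to reproduce here: 50 is declared a convenience sample, without power or an alternative rate. The question is whether selected timing can move the pooled rate away from the rate under assigned early start, and in which circumstances.

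**Inputs.** All are assumed for illustration; none comes from the protocol.

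- Risk of the primary event with later start: 1% with small and 5% with large infarcts.
- Half of the patients start early. Of these, 90% have small infarcts; of later starters, 50% do.
- Overall share of small infarcts: 0.5 × 90% + 0.5 × 50% = 70%.

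**No effect of timing.**

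- Early starters: 0.9 × 1% + 0.1 × 5% = 1.4%.
- Later starters: 0.5 × 1% + 0.5 × 5% = 3.0%.
- Pooled: 0.5 × 1.4% + 0.5 × 3.0% = 2.2%.
- All assigned to early start: 0.7 × 1% + 0.3 × 5% = 2.2%.

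The pooled rate equals the rate under assigned early start, so there is no bias.

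**Early start doubles the risk.**

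- Early starters: 2 × 1.4% = 2.8%. Later starters: 3.0%.
- Pooled: 0.5 × 2.8% + 0.5 × 3.0% = 2.9%.
- All assigned to early start: 2 × 2.2% = 4.4%.

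The pooled rate is 1.5 percentage points too low for assigned early start. Not all of that is selection. If half had started early irrespective of infarct size, the pooled rate would be 0.5 × 4.4% + 0.5 × 2.2% = 3.3%. So 1.1 points arise because later starters are in the pool, and 0.4 points because the early starters are selected.

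**Other assumed values.** Here 20% of infarcts are large, and early start doubles the risk. The last column is twice the pooled rate without a timing effect.

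| Risk small / large | Early start, small / large | Pooled | All early |
|---|---|---|---|
| 0.5% / 5% | 80% / 10% | 1.82% | 2.8% |
| 0.5% / 5% | 90% / 0% | 1.76% | 2.8% |
| 1% / 5% | 80% / 10% | 2.54% | 3.6% |
| 1% / 5% | 90% / 0% | 2.52% | 3.6% |
| 1% / 8% | 80% / 10% | 3.20% | 4.8% |
| 1% / 8% | 90% / 0% | 3.12% | 4.8% |

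The pooled rate is 63% (1.76/2.8) to 71% (2.54/3.6) of the rate under assigned early start.

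**What 50 patients can show.** At 2%, the expected number of events is 50 × 0.02 = 1.0, and the chance of none is 0.98^50 = 36%. With no event, the exact one-sided 95% upper limit is 5.8%. Even the best possible result would therefore not exclude the 4.4% of the illustration. Stratifying is no remedy: with no event among 25 patients the limit is 11.3%, and among 10 it is 25.9%.

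**The case against.** The strongest objection is that the protocol plans no comparison of early with later starters. It defines early as the whole 14-day window in the summary, 2.1 and 5.0, so the deferred starts at 5 to 14 days are inside the cohort, and 7.0 tests one pooled rate. This stands, and it rules out three stronger readings.

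- A reader might infer that selection makes the planned rate too low in any event. It does not: without a timing effect the pooled rate is unbiased, as shown above. The gap between 1.4% and 3.0% belongs to a contrast that the protocol does not plan.
- A reader might infer that the later trial would assign early start whatever the infarct size, or would take the registry's rate among early starters as its planning value. Section 1.1 says neither, and such a trial could restrict or stratify by infarct size.
- A reader might infer that the fault is a missing table of outcome by start day and infarct volume, or that such a table would justify the safety claim. The table could stand in a statistical analysis plan that is not at hand, so its absence is no finding. With about one expected primary event, it could not support an adjusted comparison either.

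Two further objections stand in part. Section 4.1 admits only minor stroke or TIA, which narrows the range of infarct size and may weaken the selection. But the protocol summary and 3.0 omit the word minor, and 4.1 sets no NIHSS or volume limit, so some spread may remain. The protocol also says openly that timing is the physician's decision and calls the study an uncontrolled registry. It does not carry this over to the haemorrhage claim, where 2.1 states its conclusion without reservation.

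**Conclusion.** The point holds as an overclaim in 2.1 and is minor. A single-arm rate under physician-selected timing cannot establish that early timing is safe, nor that early initiation is not associated with more haemorrhage. Under the assumptions above, a true doubling of risk with early start would leave the pooled rate at about two thirds of the rate under assigned early start (2.9% against 4.4%). With no timing effect there is no understatement. The size rests on assumed risks, infarct mix and selection. The selection itself rests on 1.1, 4.1 and 5.0. The rate remains a valid, if imprecise, estimate of what happens when apixaban is started within 14 days under current practice.

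**What to change.** In 2.1, make three changes:

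1. Replace the claim to demonstrate safety, and the hypothesis of no association, with an aim to estimate the rate of symptomatic haemorrhagic transformation *when apixaban is started within 14 days at a time chosen by the treating physician*.
2. Extend the existing caveat about the uncontrolled design from ischaemic events to haemorrhage.
3. State that this rate is not the rate to be expected under assigned early start in the later randomised trial.

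As support only, describe start day against baseline infarct volume and baseline NIHSS, and list any haemorrhagic transformation by both. Make no adjusted or between-group comparison. Infarct volume (9.0), NIHSS (6.1) and onset time (4.1) are already provided for, and the start date is needed anyway for the 30-day window of the primary outcome.

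The cost is a few sentences and one descriptive display. Sample size and procedures do not change. The downside is a narrower claim.

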## 2.0 Study Objectives

### 2.1 Overall Aim and Hypothesis

The primary aim of the Eliquis Acute Stroke Safety Evaluation registry is to demonstrate the safety of early anticoagulation with apixaban following cardioembolic stroke and TIA. Safety will be established by demonstrating low rates of hemorrhage in this setting. The secondary study objective is to document the rate of recurrent cerebrovascular ischemic events. It is fully recognized that this uncontrolled registry study is not properly designed and underpowered to demonstrate a reduction in cerebrovascular ischemic events.

We hypothesize that early initiation of apixaban within the first 14 days of stroke or TIA is not associated with increased symptomatic intracranial haemorrhage.

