## 3.0 Study Design

The Eliquis Acute Stroke Safety Evaluation (EASSE) is an investigator initiated, prospective, open label, single arm phase IV study.

Consecutive patients with atrial fibrillation (new onset or previous history) with acute ischemic stroke or TIA will be screened from Emergency Department or stroke unit. A total of 50 male and female patients will be recruited within 24 hours of initiation of apixaban after TIA or stroke. Informed consent will be obtained from the patient or substitute decision maker, in all cases prior to enrolment. Patients will be approached by the Stroke team or stroke unit attending physicians participating in the trial.

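### Section 2.1 hypothesizes no increase in haemorrhage, but the study has one arm and an unsourced 2% reference, so no result can establish that claim.

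*Protocol*

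**What the plan says.** The hypothesis in section 2.1 of the protocol is that "early initiation of apixaban within the first 14 days of stroke or TIA is not associated with increased symptomatic intracranial haemorrhage". The same section, like the first aim in the Protocol Summary, sets out to demonstrate safety and says how: "Safety will be established by demonstrating low rates of hemorrhage in this setting".

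Section 3.0 describes an "investigator initiated, prospective, open label, single arm phase IV study". No control group, matched cohort or named historical series appears anywhere in the protocol.

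Section 2.1 admits a limit of this design for one outcome only: "this uncontrolled registry study is not properly designed and underpowered to demonstrate a reduction in cerebrovascular ischemic events". It makes no such statement for haemorrhage.

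Section 7.0 gives the only numerical reference. The null hypothesis is a frequency below 2%, to be tested with a one-sample t-test in a convenience sample of 50. No source is given for the 2%. Section 1.1 reports "insufficient data in the present literature to indicate what the true event rates for both symptomatic hemorrhagic transformation" and recurrent cerebral ischemia are, and says that a randomized comparison of early and delayed apixaban would be the ideal way to answer the question.

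**The concern.** The hypothesis is comparative. It says that haemorrhage is no more frequent with early apixaban than it would otherwise be, whether with a later start, with no anticoagulation, or in some historical series. The protocol does not say which, and the design supplies none of them.

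At stake is what the trial may conclude. With few or no events, the wording of section 2.1 invites the statement that early apixaban does not increase haemorrhage. The data could support only a statement about the absolute rate in the patients who were enrolled.

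**Working it through.** **1. Is there a comparator?** Section 2.1 needs a reference for the word increased. Section 3.0 provides one arm. Sections 2.1, 4.1 and 5.0 all define early as a start within 14 days, and no contrast between starting times inside that window is planned. The difference from any other strategy is therefore not identified, whatever the event count.

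**2. Can the 2% stand in for one?** It has no stated source, and section 2.1 does not refer to it. The only haemorrhage difference quoted in section 1.1 is a 1.7% increase. That figure concerns heparin and hemorrhagic transformation in general, not apixaban and the primary endpoint.

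**3. If 2% is accepted, what can 50 patients show?** Inputs from section 7.0: n = 50 and reference 2%. The protocol gives no significance level or sidedness, so one-sided 0.05 is assumed. It states no derivation of the 50, so there is no figure of its own to reproduce.

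*Evidence against 2%*

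- Exact binomial: P(X ≥ 3 | n = 50, p = 0.02) = 0.078 and P(X ≥ 4) = 0.018. Four or more events (8%) reject.
- Stated t-test: t = (p̂ − 0.02) / √(p̂(1 − p̂)/49), on 49 degrees of freedom.
  - Four events: 0.06/0.0388 = 1.55, p = 0.064.
  - Five events: 0.08/0.0429 = 1.87, p = 0.034. Five or more events reject.
- Power of the exact rule: 24% at a true rate of 5%, 57% at 8% and 75% at 10%.

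*Evidence for a rate below 2%*

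- The best possible result is 0/50. The exact (Clopper-Pearson) upper limit is 1 − α^(1/50).
  - Two-sided 95%: 1 − 0.025^(1/50) = 7.1%.
  - One-sided 95%: 1 − 0.05^(1/50) = 5.8%.
- With one event, the two-sided upper limit is 10.6% and the one-sided limit 9.1%.
- If the true rate were exactly 2%, no events would be seen with probability 0.98^50 = 0.36. A clean result is thus unremarkable at the reference rate itself.
- At 0/50 the sample standard deviation is zero and the stated t-test is undefined.
- For zero events to put the one-sided 95% upper limit below 2%, n must be at least ln(0.05)/ln(0.98) = 148.3, that is 149 patients.

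With the null hypothesis on the safe side (below 2%), failure to reject is not evidence of safety either.

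**4. Could a low rate arise without any effect of timing?** Section 4.1 admits minor ischemic stroke or TIA (the Summary omits the word minor) and requires that the treating physician has prescribed apixaban. The physician also decides the timing, independently of the registry. A low count may therefore reflect who was enrolled. The figures in step 3 would improve with more patients, but steps 1, 2 and 4 would not change.

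**The case against.** The best defence is that the protocol does not offer this study as a definitive comparison. Section 1.1 points to a randomized trial as the real answer, section 7.0 calls the data initial and meant for planning, and section 2.1 defines safety by low rates, which is an absolute criterion. This has weight: a single-arm study is a sound way to obtain those rates, and the design is not the fault. What the defence does not remove is the comparative hypothesis, the aim to demonstrate safety, and a concession confined to ischemic events.

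Three stronger readings are tempting, but the protocol does not support them.

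- *That no result could bear on the hypothesis in either direction.* Section 7.0 supplies a reference, and four or five events would count against it. That would be an excess over an unsourced figure, not over delayed treatment, but it would be adverse evidence.
- *That the protocol itself says no valid background rate exists.* Section 1.1 says only that the data are insufficient, and adds that prospective collection in treated patients can supply them. The gap may well concern early-treated patients, whom this study observes.
- *That early starters are picked mainly for small infarcts.* Section 1.1 does say: "In patients with small infarct volumes, assessed with CT or MRI, however, anticoagulation is often begun within 24-72 hours of stroke onset". It also describes deferral of 5 to 14 days for extensive infarcts. Both fall inside the 14-day window, so this describes timing among eligible patients and not who is eligible. The selection argument rests on section 4.1 instead.

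It is also fair to say that 7.1% measures precision and not the lack of a comparator. It is given because it shows that the favourable claim is out of reach even if 2% is accepted as the benchmark.

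**Conclusion.** Wrong as written. The hypothesis and aim in section 2.1 claim more than a single-arm study with an unsourced 2% reference can deliver. Results can count against 2%, though with low power for moderate excesses; none can establish that haemorrhage is not increased. The most favourable outcome, 0/50, is still compatible with a rate of up to 7.1% (two-sided 95%) or 5.8% (one-sided).

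The event thresholds and the power figures assume one-sided testing at 0.05, which the protocol does not state. The confidence limits depend only on n = 50, the chosen confidence level and full ascertainment of the endpoint. The lack of a comparator depends on none of these. How the results will in fact be reported is unknown; the point is what the stated hypothesis would allow.

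**What to change.** - **Aim and hypothesis.** Reword section 2.1 and the first aim in the Protocol Summary to estimating the absolute 30-day rate of symptomatic hemorrhagic transformation, with an exact (Clopper-Pearson) confidence interval, in patients whose physicians chose to start apixaban within 14 days. Delete the claim of no association with increased haemorrhage.
- **Limitation.** Extend the statement in section 2.1 about the uncontrolled design so that it covers haemorrhage as well as ischemic events.
- **Reporting.** Give the rate alongside baseline NIHSS (section 6.1) and infarct volume (section 9.0), both already collected, so that the risk profile of the enrolled patients is visible. Add the time from onset to first dose to the list in section 6.1. The 14-day criterion implies it, but it is not listed there.
- **Section 7.0.** Bring it into line by making the rate and its exact interval the primary result.

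This needs changes of wording and one added data item. Neither the sample size nor treatment changes. The price is a more modest stated claim. If the sponsor prefers to keep a claim against a benchmark, the benchmark needs a source and the null hypothesis must be a rate at or above it. At 2%, 50 patients would not suffice: as shown above, at least 149 without a single event would be required.
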